**Table 7.1.1 Grading of Adverse Event Severity**

Grade	Adjective	Description
1	Mild	Asymptomatic or mild symptoms; clinical or diagnostic observations only; intervention not indicated.
2	Moderate	Moderate; minimal, local or noninvasive intervention indicated; limiting age-appropriate instrumental activities of daily living (i.e., preparing meals, shopping for groceries or clothes, using the telephone, managing money, etc.)
3	Severe	Severe or medically significant but not immediately life-threatening; hospitalization or prolongation of hospitalization indicated; disabling; limiting self-care activities of daily living (i.e., bathing, dressing and undressing, feeding self, using the toilet, taking medications, and not bedridden.)
4	Life-threatening	Life-threatening consequences; urgent intervention indicated.
5	Death	Results in death due to the AE

**Timing:** Non-serious AE will be reported from the initial treatment with \*Study Drug through the completion of the study Day 35. Adverse events will be captured 28 days post the last dose of study drug for participants who receive study drug and terminate early from the trial. This can be completed via a phone call. All ongoing AE's related to study drug (FCM or ferrous sulfate) should be followed until they are no longer related, have taken a confounding medication or return to baseline grade

**Relationship (Causality):** The Investigator will be asked to document his/her opinion of the relationship of the event to the study drug\* as follows:

- NONE            There is *no* evidence of any causal relationship.

- **UNLIKELY** There is *little* evidence to suggest there is a causal relationship. There is *another reasonable explanation* for the event (e.g., the participant's clinical condition, other concomitant treatments).
- **POSSIBLE** There is some evidence to suggest a causal relationship (i.e., there is a reasonable possibility that the adverse experience may have been caused by the agent). However, the influence of other factors may have contributed to the event (e.g., the participant's clinical condition, other concomitant events).
- **PROBABLE** There is evidence to suggest a causal relationship, and the influence of other factors is unlikely.

\* For the purposes of this trial, "study drug" is defined as:

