### 2.3.4 Handling of Missing Data

A participant who withdraws from the study for any reason will be included in the analyses regardless of time on study. Methods for handling withdrawals and missing data will be specific to each endpoint to be analyzed. Missing data will not be imputed for descriptive statistical summaries in safety or efficacy.

For statistical inferential (models) analyses, missing data will be imputed using last observation carried forward (LOCF) method for hemoglobin and other efficacy endpoints. e.g. for primary endpoint, hemoglobin, when Day 35 data is missing (subject has discontinued before Day 35, or measurement not taken at Day 35 though subject was not discontinued), Day 28 result will be carried forward. If the post-baseline value of the first scheduled visit is missing, the worst value obtained from the same time point of all subjects in ITT population will be used for both treatment groups. The worst value is defined as the lowest value for hemoglobin, ferritin, TSAT and reticulocyte hemoglobin content.

Supportive analyses will assess the impact of missing values on inferences based on primary efficacy endpoints and missing data will be handled by using missing at random (MAR) in

mixed effect model repeat measurement (MMRM) model. The observed case will also be applied for primary analysis.

Dates missing the day or both day and month of the year will adhere to the following conventions to classify TEAE and to classify prior/concomitant medications.

- A medication with a completely missing start date will be considered a prior medication. A medication with a completely missing stop date will be considered a concomitant medication.
- If complete AE onset date is missing and AE end date is on or after the first dose date then it will be counted as a treatment emergent AE (TEAE) for the study. If complete AE onset date is missing and AE end date is before the first dose date then it will be counted as a not treatment emergent AE (TEAE) for the study.
- If an AE or a medication has a partial missing start or stop date, the following rules will be used for imputation:
  - If year is present but month and day are missing, impute start date as January 1 of that year or first dose date if the year is the same as the year of first dose date and impute stop date as December 31 of that year.

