  - If year and day are present but month is missing, impute start month as January or the month of the first dose date if the year and day is the same as the year and day of first dose date and impute stop month as December.
  - If year and month are present but day is missing, impute start date as first day of that month or first dose date if the year and month are the same as the year and month of first dose date and impute stop date as last day of that month.

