## 7.2 ADVERSE EVENTS

Adverse events (AEs) will be coded by System Organ Class (SOC) and Preferred Term (PT) using the Medical Dictionary for Regulatory Activities (MedDRA) dictionary. The verbatim term will be included in the AE listings. Adverse event summaries will exclude preferred terms that describe asymptomatic serum ferritin, TSAT, and reticulocyte values (or changes). This approach is justified by the reporting of these values in efficacy summaries and is consistent with the protocol-defined reporting standards for hemoglobin/hematocrit and low iron indices. For the purposes of this study, non-serious anemia (hemoglobin or hematocrit below the normal range or worsened from baseline) or iron deficiency (iron indices below the normal range or worsened from baseline) will not be considered adverse events. Anemia or iron deficiency will be considered end points if an intervention is required.

A treatment-emergent adverse event (TEAE) is defined as an event with onset date on or after the study drug start date. Partial date TEAE classification rules refer to Section 2.3.4. Only TEAEs will be included in summary tables by treatment group.

The incidence of TEAEs will be summarized as the number (percentage) of subjects with TEAEs within SOC and PT by treatment group. Subjects who report the same PT on multiple occasions will be counted once for the PT: under the highest severity (severe > moderate > mild) CTCAE when summarized by severity and under the closest relationship (probably related > possibly related > unlikely related > none) to study drug when summarized by relationship. If a subject reports multiple PT for a SOC, the subject will be counted only once for that SOC. Events with unknown severity or relationship will be counted as unknown.

TEAEs will be summarized as below.

- An overview table, including number of subjects with
  - TEAEs
  - serious TEAEs
  - study drug related TEAEs
  - study drug related Serious TEAEs

- TEAEs by severity
- TEAEs leading to study drug discontinuation or withdrawal from study
- TEAEs leading to death
- TEAE by SOC
- TEAE by PT
- TEAE by SOC and PT
- TEAE by SOC, PT, and Severity(CTCAE)
- Study drug related TEAEs by SOC, PT
- Serious TEAEs by SOC and PT
- Study drug related serious TEAEs by SOC and PT
- TEAEs leading to study drug discontinuation or withdrawal from study by SOC and PT
- TEAEs leading to death by SOP and PT

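### When only the month of an adverse event's onset is missing, SAP 2.3.4 usually dates a same-year event before the first dose and removes it from the TEAE tables, unlike the neighbouring rules

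*SAP*

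**What the plan says.** SAP 2.3.4 has three rules for a partly missing start date and one for a completely missing adverse event onset.

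- **Month missing, year and day known:** "If year and day are present but month is missing, impute start month as January", with the exception "or the month of the first dose date if the year and day is the same as the year and day of first dose date".
- **Month and day missing:** 1 January of the year, "or first dose date if the year is the same as the year of first dose date".
- **Day missing:** the first of the month, "or first dose date if the year and month are the same as the year and month of first dose date".
- **Onset completely missing:** "If complete AE onset date is missing and AE end date is on or after the first dose date then it will be counted as" treatment-emergent.

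SAP 7.2 says that a TEAE "is defined as an event with onset date on or after the study drug start date", refers partial dates back to 2.3.4, and states: "Only TEAEs will be included in summary tables by treatment group". SAP 7.2.1 tabulates treatment-emergent events of special interest. SAP 7.2.2 separately lists adverse events, serious events, events leading to discontinuation, and deaths.

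On collection, Protocol 7.1 (Timing) states: "Non-serious AE will be reported from the initial treatment with" study drug, and runs to Day 35. Protocol 7.3 starts serious event reporting at the first dose too.

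**The concern.** By design, a recorded adverse event began on or after the first dose. An imputation rule should not override that unless the known parts of the date contradict it. Two of the partial-date rules respect this: where the known parts agree with the first-dose date, they use that date and the event stays treatment-emergent. The month-missing rule protects an event only if its day of month happens to equal the dosing day. Otherwise it reverts to January, which precedes dosing for most of the year.

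A record with a known day is thus treated worse than one with the year alone, or than one with no onset date and a post-dose end date. The end-date rule cannot rescue it, because that rule covers only a completely missing onset.

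At stake is the count in the TEAE, serious TEAE and special-interest tables. With 36 children planned per arm, one lost participant-level event changes an arm's incidence by 1/36 = 2.8 percentage points, always downwards.

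**Working it through.** The plan gives no figure on this point, so there is none to reproduce.

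**One record.** First dose 15 June 2020; true onset 22 June 2020, recorded as day 22, month unknown, 2020.

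1. The year matches the first dose, but day 22 differs from day 15, so the exception does not apply.
2. The imputed onset is 22 January 2020.
3. That is before 15 June 2020, so the event is not a TEAE under SAP 7.2.
4. Had the day also been missing, the imputed onset would have been 15 June 2020 and the event a TEAE.

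**All records.** Inputs from the documents are the month-missing rule and its exception (SAP 2.3.4), the TEAE definition (SAP 7.2), and collection from first dose to Day 35 (Protocol 7.1). Two assumptions are not in the documents: first doses uniform over the calendar year, and onsets uniform over Days 0 to 35. Every first-dose date was paired with every onset day, the month was masked, and the rule was applied. An event is lost if its imputed onset is earlier than the first dose.

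| First-dose year | Pairs | Lost | Share lost |
|---|---|---|---|
| 2019 | 365 × 36 = 13,140 | 11,251 | 85.6% |
| 2020 | 366 × 36 = 13,176 | 11,280 | 85.6% |
| 2021 | 365 × 36 = 13,140 | 11,251 | 85.6% |

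**By month of first dose.**

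- *February to November:* about 94%. Typically only two of the 36 onset days share the dosing day of month (Day 0 and the same date one month later), so 34/36 = 94.4% are lost. November is slightly lower (93.5%) because a few onsets fall in the next year.
- *December:* 42%. There are 31 × 36 = 1,116 pairs. For a dose on December d, d + 4 onset days fall in the next year and stay treatment-emergent; summed over d = 1 to 31 this is 496 + 124 = 620. The 31 Day 0 onsets are also kept. This leaves 1,116 − 620 − 31 = 465 lost, and 465/1,116 = 41.7%.
- *January:* 44%, because a January imputation often still falls after the dose.

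**Sensitivity to onset timing.** The share lost is 80.1% for onsets on Days 0 to 7 and 88.1% if Day 0 is excluded. Day 0 onsets are never lost, because their day of month matches.

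**The other partial-date rules on the same grid.** Month and day missing: 0 lost. Day missing: 0 lost.

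**The rule proposed under the fix on the same grid.** 0 of 13,140 lost (0 of 13,176 in 2020). This must be so: for a same-year post-dose onset the true month always qualifies, so an earliest qualifying month exists.

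**The case against.** The strongest reply is that the pattern may never occur. Participation lasts about 6 weeks, adverse events are assessed on Days 0, 7, 14, 28 and 35, investigators record the date and time of onset, and serious events are reported within 24 hours of being learned of. A date with a known day and year but no month is unusual in such a setting, and nothing in the documents predicts any. This stands, and it is why the point is minor. It does not make the rule right: the SAP chose to write one for this case, and it gives the wrong answer.

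The 86% is also conditional on two assumptions and moves with them, as shown. That stands too.

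A reader might infer more than the documents support:

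- *That the event vanishes from safety reporting.* It does not. The SAP 7.2.2 listings should keep it, and the laboratory tables in SAP 7.3 do not depend on adverse event onset dates.
- *That 86% of adverse events are at risk.* The figure applies only to records lacking the month alone.
- *That reactions on the first dosing day are lost.* The exception protects Day 0 onsets. It does not protect a reaction at the Day 7 dose.
- *That the lost events are all on treatment.* FCM is given on Days 0 and 7 and oral iron for 28 days, while collection runs to Day 35. The accurate description is on or after the first dose.

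Finally, the lead-in to these conventions in SAP 2.3.4 mentions dates lacking the day, or the day and month, but not the month alone. One could argue that the bullet lies outside its own scope. That is a further inconsistency to repair, since the bullet plainly addresses the case.

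**Conclusion.** The rule is wrong as written; severity is minor. For same-year events it conflicts with the protocol's collection window and with the neighbouring rules in the same section, and its error always removes events from the TEAE tables. The expected number of affected records is small and cannot be estimated from the documents. Given such a record, about 86% of post-dose onsets are misclassified under uniform dosing over the year and uniform onset over Days 0 to 35, ranging from 42% (December dosing) to about 94% (February to November dosing). The direction of the error does not depend on those assumptions.

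**What to change.** In SAP 2.3.4, separate adverse event onset from medication start for the month-missing case.

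- **Adverse event onset:** if the year equals the first-dose year and the month is missing, impute the earliest month in that year that puts onset on or after the first dose. If no month does so (for example, first dose 20 December, onset day 10 of the same year), or if the end date is before the first dose, class the event as not treatment-emergent.
- **Medication start:** leave the rule unchanged. Protocol 5.5 records medications from 30 days before consent, so a pre-dose start is plausible, and the new rule could move true prior starts to after dosing.
- **Lead-in:** add dates missing only the month, so that it agrees with the bullet.

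The cost is a sentence or two in the SAP and the matching line of date-derivation code. No extra data are needed, and the change can be made before database lock.

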## **2.4 POOLING OF CENTERS**

The study centers are not planned to be used as a stratification factor nor a covariate in the statistical modeling and testing, therefore it is not necessary to pool small centers together.

## **2.5 ANALYSIS SOFTWARE**

All summaries and statistical analyses will be generated using SAS® version 9.4 or higher.

## **3. STUDY SUBJECTS**

### **3.1 DISPOSITION OF SUBJECTS**

Disposition will be summarized by treatment group and overall for all enrolled subjects and also summarized in each investigative site.

The disposition will include the following:

- Participants who are randomized (= ITT population)
- Participants who are in Safety Population
- Participants who complete the study
- Participants who discontinue the study

The number and percent of subjects will be summarized for each reason for premature discontinuation based on the ITT population.

A listing of dispositions will be provided for all randomized subjects. In addition, a listing of randomization will also be provided.

### **3.2 PROTOCOL DEVIATIONS**

The clinical team will identify deviations and the deviations will be identified in the database prior to database lock. The number and percent of participants with clinically important protocol deviations will be summarized for each type of deviation by treatment group and overall based on the ITT population.

A listing of inclusion/exclusion criteria violations and a listing of all protocol deviations will be provided.

### **3.3 CONCOMITANT INTERVENTION**

Concomitant intervention is defined as follows:

- Blood transfusion.
- Use of IV or oral iron outside of protocol.
- Increase in erythropoietin for any reason (Day 0 thru Day 35).
- Change in IBD treatment

The interventions mentioned above are non-study interventions. When concomitant intervention occurs, the date of the intervening event should be recorded in the source documents, and the electronic Case Report Form (eCRF). The participant should continue in the study as scheduled. The number (percentage) of subjects who have concomitant intervention will be summarized by treatment group and overall for ITT population.

## **4. DEMOGRAPHY AND BASELINE CHARACTERISTICS**

### **4.1 DEMOGRAPHY AND BASELINE CHARACTERISTICS**

Demography data such as sex, age, age group (1 to <12 and  $\geq 12$  to 17 years), race, ethnicity, body height, body weight, BMI and BMI group (underweight  $\leq 18.5$ ,  $18.5 < \text{normal weight} \leq 24.9$ ,  $25 < \text{overweight} \leq 29.9$ , obesity = BMI of 30 or greater) will be summarized with descriptive statistics or frequency counts by treatment group and overall for all patients in ITT and Safety populations..

The following disease-specific baseline characteristics will also be summarized with descriptive statistics or frequency counts by treatment and overall for ITT and Safety populations,

- Cause of IDA
- Baseline hemoglobin and the categories (baseline hemoglobin <10 g/dL, baseline hemoglobin ≥10 g/dL).
- Status of IV iron intolerance
- Status of oral iron tolerance response
- Status of drug allergy/intolerance (other than iron)

A subject data listing of demographics and baseline characteristics will be provided.

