#### 4.2.1 Inclusion Criteria

1. Male or female participants 1 to 17 years of age with assent to participation and his/her parent or guardian is willing and able to sign the informed consent approved by the Independent Review Board / Ethics Committee.
2. Screening hemoglobin <11 g/dL.
3. Screening ferritin  $\leq$  300 ng/mL and TSAT <30%.
4. Documented history of an inadequate response to any oral iron therapy for at least 8 weeks (56 days) prior to randomization.
5. If receiving an ESA: stable ESA therapy (+/- 20% of current dose) for at least 8 weeks prior to the qualifying screening visit and no ESA dosing or product changes anticipated for the length of the trial.
6. If undergoing treatment for IBD must be on stable therapy for at least 8 weeks prior to consent.

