#### 2.1.1 Reporting Precision

Summary statistics will be presented to the following degree of precision, unless otherwise specified:

Statistics	Degree of Precision
------------	---------------------

Mean, Geometric mean, Median, Quartiles, Confidence limit boundaries	One decimal place more than the raw data.
Standard deviation, Standard error	Two decimal places more than the raw data.
Minimum, Maximum	The same as the raw data.
p-value	Rounded to 4 decimal places and therefore presented as 0. xxxx; p-values smaller than 0.0001 as '<0.0001'; p-values greater than 0.9999 as '>0.9999'.
Percentage	One decimal place. A percentage of 100% will be reported as 100%. Percentages of zero will be reported as 0.

For weight and height, one decimal place will be used for summary statistics. Fractional numeric values will be presented with a zero to the left of the decimal point (for example, 0.12 – 0.30).

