## **7.4 VITAL SIGNS AND PHYSICAL EXAMINATION FINDINGS**

### **7.4.1 Vital Signs**

Vital signs will be collected including sitting body temperature, blood pressure (BP) and heart rate. On study drug dosing days BP and heart rate will be collected pre-dosing, immediately (within 5 minutes) post, and 30 minutes post dosing, and body temperature will be collected on each dosing day. For the FCM group, the actual value and the change in vital signs (including sitting heart rate and blood pressure) from pre-infusion to each post-infusion time point will be summarized descriptively on each dosing day. Markedly abnormal values should be determined by PALS Guidelines, 2015 in Appendix 1.2. Children >15 years of age will use the criteria for 15 years old children.

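### One age- and sex-independent set of BMI groups is applied to participants aged 1 to 17, and its limits leave gaps, so the BMI-group rows of the baseline table are age-confounded and incomplete.

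*SAP*

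**What the plan says.** SAP 4.1 lists the demographic variables to be summarised. Among them are height, weight, "BMI and BMI group (underweight" and three further groups. The limits are:

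- underweight: 18.5 or below
- normal weight: above 18.5, up to and including 24.9
- overweight: above 25, up to and including 29.9
- obesity: "obesity = BMI of 30 or greater"

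These are reported "by treatment group and overall for all patients in ITT and Safety populations". Protocol 4.2.1 defines who those patients are: "Male or female participants 1 to 17 years of age". No age or sex term enters the grouping, and no source is named for the limits.

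On rounding, SAP 2.1.1 says "For weight and height, one decimal place will be used for summary statistics". It gives no rule for the precision of an individual BMI before it is assigned to a group.

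The protocol does not define BMI groups, and SAP 9 does not mention them among its major changes.

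**The concern.** There are two separate faults in one rule.

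First, a 1-year-old and a 17-year-old with the same BMI get the same label. BMI in childhood is normally read against age and sex. A fixed limit across this range sorts participants partly by how old they are. The SAP adjusts for age elsewhere. For vital signs, "Markedly abnormal values should be determined by PALS Guidelines, 2015 in Appendix 1.2", and that chart is banded by age. In Appendix 1.1 the reference limits for alkaline phosphatase, ALT, AST and creatinine are given by age and sex, and those for albumin by age. BMI group has no such adjustment, and no reason is given.

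Second, the four intervals do not cover the scale. A programmer who follows the text will meet values with no group and no instruction. The hemoglobin categories in the same section (below 10, and 10 or above) are contiguous, so this looks like a drafting slip.

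What is at stake is the accuracy of a reported baseline table. Protocol 1.1 names poor weight gain and anorexia among the consequences of iron deficiency in children, so a reader may well use these rows to judge nutritional status.

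**Working it through.** **Inputs.** The four limits come from SAP 4.1 and the age range from Protocol 4.2.1. The documents give no BMI, height or weight distribution for any age, so anything that needs one is an assumption and is shown over a range. The plan has no computed figure on this point to reproduce.

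**Step 1: do the groups cover every value?** Each BMI from 10 to 45 was tested against the four inequalities exactly as written.

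| Precision of BMI | Values in no group | Values in two groups |
|---|---|---|
| One decimal | 1 (25.0) | 0 |
| Two decimals | 19 (24.91 to 25.00, and 29.91 to 29.99) | 0 |

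The two-decimal count is 10 + 9 = 19. On a continuous scale, the gaps run from just above 24.9 up to and including 25, and from just above 29.9 to just below 30. At one decimal the second gap contains no values. As an example of the first, a child of 1.20 m weighing 25.0 × 1.20² = 36.0 kg has a BMI of exactly 25.0 and belongs to no group.

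**Step 2: what does the underweight limit require?** To leave that group, weight must exceed 18.5 × height².

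- 1.00 m: 18.5 × 1.00 = 18.5 kg
- 1.10 m: 18.5 × 1.21 = 22.4 kg
- 1.20 m: 18.5 × 1.44 = 26.6 kg

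A child of 1.00 m and 16 kg has BMI 16 / 1.00² = 16.0 and is labelled underweight whatever the child's age. This shows how the rule works. It does not show how many participants are affected.

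**Step 3: how many in the younger stratum might be labelled underweight?** If BMI is Normal with mean m and standard deviation s, the share is Φ((18.5 − m)/s).

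| Assumed mean | SD 1.5 | SD 2 | SD 3 |
|---|---|---|---|
| 16 | 95% | 89% | 80% |
| 17 | 84% | 77% | 69% |
| 18 | 63% | 60% | 57% |
| 19 | 37% | 40% | 43% |
| 20 | 16% | 23% | 31% |

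For example, with m = 16 and s = 2, (18.5 − 16)/2 = 1.25 and Φ(1.25) = 0.894. The share passes one half exactly when the mean (here also the median) falls below 18.5.

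**Step 4: where else is BMI group used?** The randomization strata are hemoglobin and age (SAP 1.3.2). The primary model has treatment, those strata and baseline hemoglobin (SAP 6.1.1). The subgroups are hemoglobin and age (SAP 6.1.2). Doses use weight or a fixed tablet (Protocol 5.2). BMI group enters none of these.

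**Step 5: would contiguous limits close the gaps?** With below 18.5; 18.5 to below 25; 25 to below 30; and 30 or above, every value from 10.00 to 45.00 falls in exactly one group. The age problem remains.

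**The case against.** The strongest reply is that very little depends on these rows. SAP 4.1 also summarises age, height, weight and BMI itself by arm, and promises a subject listing. Randomization is stratified by age at 12 years, which limits any age-driven difference in BMI labels between arms. With about 72 participants, few or none may fall in a gap. Someone who does would still appear in the continuous BMI summary, and SAP 2.1 allows unknown or missing data to be shown as a category of their own. All of that stands, and it keeps the point minor. It does not make the labels right, and an unclassified BMI is not a missing one.

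A reader might also infer more than the documents support:

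- *That most young children will be labelled underweight.* This needs a median BMI below about 18.5 in that stratum, and the documents give no BMI data.
- *That the table hides a real imbalance between arms.* Continuous BMI, weight and height by arm would still show one, although BMI pooled over ages 1 to 17 mixes age with nutritional status.
- *That weight-based dosing makes this matter more.* Dosing uses measured weight, not BMI group.
- *That a participant with a BMI of 25.0 is lost from the counts.* The SAP does not say how such a value would be shown.

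**Conclusion.** The point holds as a minor error in a stated rule. Two facts follow from the text alone: the BMI groups take no account of age or sex across ages 1 to 17, and they leave 25.0 unclassified (19 values at two decimals). That the rows would largely reflect age rests on the general premise that BMI varies with age in childhood, which the documents do not quantify. The share of the younger stratum labelled underweight is conditional: a majority if the median BMI there is below about 18.5, and a minority otherwise. The damage is limited to the BMI-group rows of one descriptive table, and no efficacy or safety conclusion changes.

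**What to change.** In SAP 4.1, replace the four groups with contiguous age- and sex-specific BMI-for-age categories, or z-scores, from one named pediatric reference that covers ages 1 to 17. If no single reference is acceptable, drop the labels and report continuous BMI by age stratum (1 to <12, and 12 to 17). At the least, make the limits contiguous as in step 5 and state the precision at which BMI is held before grouping. That closes the gaps but leaves the age problem.

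The cost is a few lines of SAP text and one derivation. Age and sex are already among the demographic variables, and height and weight are already taken at screening, so no new data are needed.
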